Patients with metastatic urothelial cancer will receive Atezolizumab intravenously at 1200mg every three weeks or Pembrolizumab at a flat dose of 200mg every three weeks (Physician's discretion). Patients will continue to receive infusions every two or three weeks for up to three years or until disease progression or until a dose limiting toxicity is reached.

Patients randomized to the radiotherapy arm will receive radiation every other day. A dose of 10 Gy x3 days will be administered.

Primary Objectives: The primary aim is to estimate the difference in best overall response (BOR; time frame: 96 weeks) rates using RECIST version 1.1, in patients with metastatic renal cell/urothelial carcinoma when treated with immunotherapy alone and immunotherapy plus radiotherapy (to a single metastatic site).

[figure not shown]
Secondary Objectives: The secondary aims are: 1) to estimate the median progression free survival and the median overall survival for patients treated with immunotherapy and immunotherapy plus radiotherapy, and 2) to assess the toxicity (per CTCAE version 4.0) of patients treated with immunotherapy and immunotherapy plus radiotherapy.

**Exploratory
(Correlatives)
Objectives:**

Exploratory analyses will include: 1) examination of an association between clinical responses and anti-tumor immune responses (cellular and humoral responses) and 2) comparison of T cell subsets within tumors and in the peripheral blood at baseline versus at the time of response evaluation.

Endpoints: The primary endpoint will be BOR (time frame: 96 weeks) rates as evaluated using RECIST version 1.1. Other end points include progression free-survival and overall survival.

SCHEMA
Please see study calendar (section 14.0) for additional screening procedures and treatment windows

- *Renal cell cancer patients – Nivolumab (flat dose of 240mg) q2 weeks up to 3 years. Immune labs to be drawn prior to infusion on Days 1, 29 and 57.
- *Urothelial cancer patients – Nivolumab (flat dose of 240mg) q2 weeks up to 3 years or Atezolizumab (1200mg) q3 weeks up to 3 years or Pembrolizumab (flat dose of 200mg) every 3 weeks up to 3 years. Immune labs to be drawn prior to infusion on Days 1, 43 and 64.
- Radiation (10 Gy x3 fractions) will be delivered on days 1, 3 and 5.
- ‡ MRI brain for patients in the RENAL Cancer cohort only.

Table of Contents

DOCUMENT HISTORY : 6

SUMMARY OF CHANGES : AMENDMENT 1 DATED 12.15.2016 6

PROTOCOL SUMMARY 7

SCHEMA..... 9

1.0 Study Objective 13

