17.3.2 Safety Assessments

All patients who receive at least one dose of Immunotherapy will be considered evaluable for safety parameters. Additionally, any occurrence of a SAE from time of consent up to and including follow-up visits will be reported. Refer to safety reporting section 6.2

Safety will be evaluated for all treated patients using the NCI CTCAE version 4.03 (<http://ctep.cancer.gov>). Safety assessments will be based on medical review of AE reports and the results of vital sign measurements, physical examinations and clinical laboratory tests.

1.12.1.1 17.4 Criteria for Evaluation

1.12.1.1.1 17.4.1 Safety Evaluation

This protocol will be monitored by the WCM Data Safety Monitoring Committee which oversees the safety of all WCM investigator initiated clinical trials. The trial will be monitored for all adverse events, laboratory abnormalities, and serious adverse events at least once every 12 months. In addition, serious adverse events are monitored for all studies on a monthly basis.

1.12.1.1.2 17.4.2 Efficacy Evaluation

For the purposes of this study, patients should be re-evaluated for response every 9 weeks, in year 1, every 12 weeks in years 2 and 3. Confirmatory scans may also be obtained 4 weeks following initial documentation of objective response or progressive disease.

Response and progression will be evaluated in this study using the international criteria proposed by the Response Evaluation Criteria in Solid Tumors (RECIST) guideline (version 1.1). Patients will be followed for scans every 9 weeks for the first year or until disease progression and every 12 weeks after the first year or until disease progression.

Measurable and non-measurable lesions:

- Measurable disease: Measurable lesions are defined as those that can be accurately measured in at least one dimension (longest diameter to be recorded) as ≥ 20 mm (≥ 2 cm) by chest x-ray or as ≥ 10 mm (≥ 1 cm) with CT scan, MRI, or calipers by clinical exam. All tumor measurements must be recorded in millimeters (or decimal fractions of centimeters).
- Malignant lymph nodes: pathologically enlarged and measurable lymph node must be ≥ 15 mm (≥ 1.5 cm) in short axis when assessed by CT scan (CT scan slice thickness recommended to be no greater than 5 mm [0.5 cm]). At baseline and in follow-up, only the short axis will be measured and followed.

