Note: If tumor markers are initially above the upper normal limit, they must normalize for a patient to be considered in complete clinical response.

Non-CR/Non-PD: Persistence of one or more non-target lesion(s) and/or maintenance of tumor marker level above the normal limits.

Progressive Disease (PD): Appearance of one or more new lesions and/or unequivocal progression of existing non-target lesions. Unequivocal progression should not normally trump target lesion status. It must be representative of overall disease status change, not a single lesion increase.

Although a clear progression of “non-target” lesions only is exceptional, the opinion of the treating physician should prevail in such circumstances, and the progression status should be confirmed at a later time by the review panel (or Principal Investigator).

1.13.1.3 18.3 Evaluation of Overall Response Criteria

The best overall response is the best response recorded from the start of the treatment until disease progression/recurrence (taking as reference for progressive disease the smallest measurements recorded since the treatment started). The patient's best response assignment will depend on the achievement of both measurement and confirmation criteria. Revised Response Evaluation Criteria in Solid Tumors (RECIST) Version 1.1

1.14 19.0 Response According to Revised Response Evaluation Criteria in Solid Tumors Version 1.1

Target Lesions	Non-Target Lesions	New Lesions	Overall Response	Best Overall Response when confirmation is Required
CR	CR	No	CR	≥ 4 weeks confirmation
CR	Non-CR/Non-PD	No	PR	≥ 4 weeks confirmation
CR	Not Evaluated	No	PR	
PR	Non-CR/Non-PD/Not Evaluated	No	PR	
SD	Non-CR/Non-PD/Not Evaluated	No	SD	Documented at least once ≥ 4 weeks confirmation from baseline
PD	Any	Yes or No	PD	No prior SD, PR or CR.
Any	PD	Yes or No	PD	
Any	Any	Yes	PD	

CR = Complete response; PD = Progressive Disease; PR=Partial response; SD =Stable disease.

1.15 20.0 Response Endpoints

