The system provides audit trails that track creation and modification of records that include user ID and timestamp. Once entered, the data is subjected to validation procedures that are executed either immediately or upon saving the eCRF page or during the batch validation process. Validation failures that are identified before the page is saved can be corrected immediately. Validation failures during saving of the eCRF page and during batch validation processes will generate a discrepancy. Depending on the database account privileges, the data managers may be able to correct a discrepancy or if not, route it to the project data manager at WCM who can take appropriate action to correct the problem. Data clarification forms can also be printed out when necessary to be sent to the project data manager. Once the discrepancy is closed, by marking “resolved” or “irresolvable”, the data is marked clean and an audit trail is generated by the system.

All key end points will be source verified by a second person and errors will be corrected. Once the data is verified and all discrepancies are closed, the data can be locked/frozen. Locking and freezing can be done at different granular levels and will follow institutional SOPs and any specific requirements for the project.

Security measures that will be taken in order to protect patient data will include firewall technology and database level security which will be achieved by assigning roles and privileges to different levels of users and by requiring that the users authenticate themselves using user ID and password. Additional security for data transfer between remote clients and servers will be achieved by using digital certificates/SSL. All data will be backed-up to tape periodically according to the Institutional SOPs. All data will be stored for at least 5 years following the termination of this study.

1.24 29.0 Statistical Considerations

112 patients will be randomly assigned in a 1:1 ratio to treatment with immunotherapy (Nivolumab or Atezolizumab) or to treatment with immunotherapy (Nivolumab or Atezolizumab) plus radiotherapy in this phase II trial. With 56 patients per group, if the expected response rate (PR or CR) is 20% with immunotherapy alone, we can detect a response rate of 40% for immunotherapy plus radiotherapy with a 1-sided alpha of 20% and a power of 90%.

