Forty patients per year will be randomized to the trial over ~ 3 years of accrual, assuming an accrual rate of approximately 20 patients per year for each cohort (see study calendar).

1.24.1.1 29.1 Statistical analysis

Both arms will run in parallel but will be analyzed separately. When the target accrual is met for a cohort, it will be closed to accrual even though other cohorts may still be accruing. Analyses will be done separately for each arm. Analyses will be similar for the two arms.

The primary objective of this study is the comparison of best overall response rates between each arm after start of treatment. Fisher's Exact test will be used to estimate 95% confidence intervals for the difference and to perform a one-sided test with an alpha level of 20%. Response rates for each arm will also be estimated at this level. With 56 patients treated under each modality, if the true responses are 20% and 40% in the immunotherapy alone and immunotherapy and radiation arms, respectively, we have a 90% probability of detecting a difference between modalities. Secondary objectives include time to disease progression and mortality. Median times for these events will be estimated with 95% confidence intervals. Graphical summaries will include Kaplan-Meier curves and log-rank tests which will be used to detect differences between treatments. Median survival and progression times will be estimated if sufficient events are observed. Cox proportional hazards regression will be used to account for baseline characteristics. Stratified exploratory analyses by type of cancer (renal cancer cell carcinoma or urothelial carcinoma) will also be performed.

Toxicities will be summarized per arm and prepared using Chi-square or Fisher's Exact tests, where appropriate.

Patient and disease characteristics will be summarized and compared at randomization between the two treatment arms using descriptive statistics and graphical displays. Although randomization will remove systematic biases we will test for differences in arms using Chi-square or Fisher's exact methods for categorical variables and t-tests or Kruskal-Wallis tests (with appropriate transformations of data if necessary for continuous variables). Differences in RECIST outcomes within each patient comparing non-irradiated and irradiated lesions will be summarized. Similar techniques will be used for exploratory analyses of the following:

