1. Distribution of changes in T cells from baseline to response evaluation.
2. Association between abscopal responses and T cell changes from baseline. Changes from baseline in immune responses will be summarized over the time course of the study and post treatment using descriptive statistics and graphical displays. The patterns of changes in immune parameters will be examined using exploratory statistical approaches to assess the relationship of changes in individual parameters to clinical outcomes. Mixed effects regression models and general estimating equations will be used to compare the patterns of change in immune response over time in the two treatment groups.

Changes from pretreatment to follow up levels of immunologic parameters and other parameters described above in irradiated tumors (and non-irradiated tumors) will be compared between the two treatment groups using descriptive statistics and graphical displays.

All patients will be followed for progression-free survival and overall survival. Kaplan-Meier curves for progression-free survival and overall survival will be provided to summarize the results.

1.24.1.2 29.2 Interim Analyses

A futility analysis will be conducted after 50% of the total 18-week RECIST responses (estimated median time to response ~14 weeks) for final analysis have occurred (i.e., N/2 of N). No accrual suspension is required to conduct the futility analysis. If at this point the relative risk of no response in the immunotherapy arm over the immunotherapy plus radiation arm is 1.0 or less, the study will be stopped for futility.

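### The futility look counts only 18-week responses although the stated median time to response is about 14 weeks, so it stops a true 20% vs 40% effect about 13–17% of the time; a later or fuller count is a cheap improvement

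*Combined protocol and SAP*

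**What the plan says.** - **Look (Section 29.2):** "A futility analysis will be conducted after 50% of the total 18-week RECIST responses (estimated median time to response ~14 weeks". The same sentence also glosses the trigger as half of N. The trial is stopped if the relative risk of no response, immunotherapy alone over combination, is 1.0 or less.
- **Endpoint (Protocol Summary, Endpoints):** "The primary endpoint will be BOR (time frame: 96 weeks) rates as evaluated using RECIST version 1.1".
- **Scans (Section 17.4.2):** "patients should be re-evaluated for response every 9 weeks, in year 1, every 12 weeks in years 2 and 3". Section 6.2 gives each scan a window of ±7 days. The first three scans therefore fall at weeks 9, 18 and 27. Section 17.4.2 makes a confirmatory scan at 4 weeks optional.
- **Confirmation (Section 18.3):** "best response assignment will depend on the achievement of both measurement and confirmation criteria". The table in Section 19 sets the interval at 4 weeks or more.
- **Design (Sections 29.0 and 29.1):** "112 patients will be randomly assigned in a 1:1 ratio", which makes 56 per arm. The control rate of PR or CR is taken as 20%. The stated aim is that "we can detect a response rate of 40% for immunotherapy plus radiotherapy with a 1-sided alpha of 20% and a power of 90"%. The final analysis is Fisher's exact test, used "to perform a one-sided test with an alpha level of 20"%.

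Section 29.2 does not say whether an 18-week response must be confirmed, or whether it is dated by first documentation or by confirmation. No section gives the chance of a false futility stop, and the power statement does not mention the look.

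**The concern.** The rule is mandatory and has no margin: the combination arm must be strictly ahead at half the sample. A rule like that is reasonably safe when the interim count carries most of the information in the final endpoint. Here the count is cut at week 18 of a 96-week endpoint, and the plan's own median implies that a sizeable share of eventual responses will appear later. With fewer events per arm, ties and chance reversals become more common even if radiotherapy doubles the response rate. The trial could then be closed on a treatment that works, at a rate the plan neither states nor allows for in its power.

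**Working it through.** **1. The plan's own figure.** With 56 per arm, rates 20% and 40%, and a one-sided Fisher test at 20%, exact power is 90.2% (actual size 14.5%). The stated 90% reproduces for a single final test with no futility stop.

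**2. The stopping rule in counts.** Let *a* and *b* be the responders among 28 control and 28 combination patients (half of 112, split 1:1; an assumption about the trigger). The relative risk of no response is (28 − a)/(28 − b). It is 1.0 or less exactly when b ≤ a, so ties stop.

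**3. Share of responses visible, f.** The plan gives only the median of about 14 weeks, so the shape is assumed.
- Exponential: f(t) = 1 − 2^(−t/14). At 18 weeks this is 0.59; at 27 weeks, 0.74.
- Log-normal: f(t) = Φ(ln(t/14)/s), with s = 0.5 to 0.7. At 18 weeks this is 0.69 to 0.64; at 27 weeks, 0.91 to 0.83.

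**4. False-stop probability.** P(b ≤ a) = Σₓ P(a = x)·P(b ≤ x), with a ~ Bin(28, 0.2f) and b ~ Bin(28, 0.4f). Overall power is simulated: the trial must pass the look, and the final Fisher test on 96-week response must reject.

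| What is counted | f | False stop | Overall power |
|---|---|---|---|
| Every eventual response | 1.00 | 6.4% | 87% |
| First documented by scan 2, exponential | 0.59 | 15.9% | 79% |
| Same, log-normal | 0.64–0.69 | 13–14% | 80–82% |
| First documented by scan 3, exponential | 0.74 | 12% | 83% |
| Same, log-normal | 0.83–0.91 | 8–10% | 85–86% |

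**5. Does requiring confirmation change this?** Only a little, because the look is a calendar event. At 40 patients a year, 56 patients take 56/40 × 52 ≈ 73 weeks to enrol. A look 18 weeks after the last of them therefore finds the earliest patients with about 90 weeks of follow-up. Three or four of the 56 lack the 4 further weeks needed to confirm a week-18 response; about 7 lack the 9 weeks to the next routine scan. Simulating this, with confirmation required and on file at the look, gives a false-stop risk of about 14–17%, against 13–16% without confirmation.

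**6. The trigger wording.** Half of the responses is not the same as half of the patients. Under the exponential model, about 33.6 × 0.59 ≈ 20 responses by week 18 are expected in total, where 33.6 = 56 × 0.2 + 56 × 0.4. Half is about 10. Treating each as falling in the combination arm with probability 2/3, P(Bin(10, 2/3) ≤ 5) ≈ 21%. The choice of trigger therefore matters too.

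**7. Does a fuller count weaken the futility rule?** Hardly. If both arms respond at 20%, the chance of stopping is about 58% with the second scan and about 57% with the third.

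**The case against.** A reader might go further and infer that only responses first seen at week 9 can qualify, because a response first seen at week 18 cannot be confirmed until week 22 or later. With a 14-week median, under half of eventual responses would then count. The false-stop risk would be at least 19% (f = 0.5), about 25% for the exponential and up to 38% for the assumed log-normal. The documents do not support that reading:

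- Section 29.2 requires neither confirmation nor a confirming scan by week 18. The confirmation rule in Section 18.3 governs the assignment of best response.
- The nivolumab efficacy table in Section 3.4 dates a confirmed response by its onset. It reports a minimum of 1.4 months (about 6 weeks), too early to be the date of a confirming scan at least 4 weeks later.
- The look is a calendar event, so nearly all confirming scans would already be on file.
- Sections 17.4.2 and 20.0 allow extra scans between the scheduled ones.

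The ±7-day window is not a separate problem either: a Day 133 scan is still the protocol's second scan, and nothing sets a strict Day 126 cutoff.

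It can also be said that the remaining effect is simply how an early look with a no-margin rule behaves, and that it overlaps with the look's absence from the power statement. That is fair as a description. It does not remove the cost, which can be reduced without weakening the rule when there is no effect.

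**Conclusion.** The point stands in a limited form. On the natural reading of Section 29.2, a true 20% vs 40% effect is stopped about 13–17% of the time, roughly double or more the 6% that applies if all eventual responses were visible. Overall power is about 78–82%, dipping to about 77% in the least favourable case (confirmation required and obtained only at the next routine scan). Even with all responses visible, the look would hold power to about 87%, so not all of the loss comes from the week-18 cut.

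The figures rest on 28 patients per arm at the look, equal response timing in both arms, no dropout, and an exponential or log-normal response time (log-SD 0.5–0.7) around the stated median. The distributions are assumptions. If responses came later in the combination arm, the risk would be higher. A risk of 19% or more would apply only if confirmation had to be complete by week 18, which the plan does not say. This is a cheap improvement, not a fatal flaw.

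**What to change.** In Section 29.2:

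1. Define the look as the first 56 randomised patients and drop the trigger based on half of the responses.
2. Count CR or PR, dated by first documentation and with confirmation not required, at any scheduled scan up to and including the third (week 27 + 7 days).
3. State the resulting false-stop probability and the overall power with the look in place.

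This gives a false-stop risk of about 8–12% and power of about 83–86%. The cost is wording plus a 9-week later look. At 40 patients a year, 56 + 40 × 27/52 ≈ 77 patients are randomised by then, against 56 + 40 × 18/52 ≈ 70. A futility stop would save about 35 patients rather than 42.

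Alternatively, keep the look date and count every response documented to date in those 56 patients. Simulated with the same accrual and response-time models, this gives a false-stop risk of about 7–9% with no delay. Follow-up then differs between patients, but randomisation balances it between arms. The confirmed 96-week best overall response stays the final endpoint under either option.

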Hazard ratio (95% CI)	0.73 ^a (0.60, 0.89)	
p-value	0.0018 ^b	
Confirmed Objective Response Rate (95% CI)	21.5% (17.6, 25.8)	3.9% (2.2, 6.2)
Median duration of response in months (95% CI)	23.0 (12.0, NE)	13.7 (8.3, 21.9)
Median time to onset of confirmed response in months (min, max)	3.0 (1.4, 13.0)	3.7 (1.5, 11.2)

^a Hazard ratio is obtained from a Cox proportional hazards model stratified by MSKCC risk group, number of prior anti-angiogenic therapies, and region with treatment as the sole covariate.

^b p-value is obtained from a two-sided log-rank test stratified by MSKCC risk group, number of prior anti-angiogenic therapies, and region. The corresponding O'Brien-Fleming efficacy boundary significance level is 0.0148.

1.5.1.5 3.5 How Supplied/Storage And Handling - nivolumab

Carton Contents	NDC
40 mg/4 mL single-dose vial	0003-3772-11
100 mg/10 mL single-dose vial	0003-3774-12

Store nivolumab under refrigeration at 2°C to 8°C (36°F to 46°F). Protect nivolumab from light by storing in the original package until time of use. Do not freeze or shake.

1.5.1.6 3.6 Drug Related SAEs: Nivolumab

1.5.1.6.1 3.6.1 Immune-mediated Pneumonitis

Immune-mediated pneumonitis, defined as requiring use of corticosteroids and no clear alternate etiology, including fatal cases, occurred with nivolumab treatment. Across clinical trial experience in patients receiving nivolumab, fatal immune-mediated pneumonitis occurred in 0.2% (5/2166) of patients. All five fatal cases occurred in a dose-finding study with nivolumab doses of 1 mg/kg (two patients), 3 mg/kg (two patients), and 10 mg/kg (one patient).

In Renal Cell Carcinoma patients, pneumonitis, including interstitial lung disease, occurred in 5% (21/406) of patients receiving nivolumab. Immune mediated pneumonitis occurred in 4.4% (18/406) of patients receiving nivolumab (one with Grade 4, four with Grade 3, twelve with Grade 2, and one with Grade 1). The median time to onset was 3.82 months (range: 2 days to 22.3 months). The median duration was 1.3 months (range: 0.3 to 9.8 months).

1.5.1.6.2 3.6.2 Immune-Mediated Colitis

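### The 90% power in sections 29.0 and 29.1 is the fixed-design figure and leaves out the mandatory futility stop in 29.2; with that rule and every response visible at the look, power is about 87–88%

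*Combined protocol and SAP*

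**What the plan says.** Section 29.0 randomizes 112 patients 1:1, takes 20% as the response rate in the control arm, and states the design's power as follows: "we can detect a response rate of 40% for immunotherapy plus radiotherapy with a 1-sided alpha of 20% and a power of 90" percent. Section 29.1 names Fisher's exact test, one-sided at 20%, and repeats the figure for 56 per arm: "we have a 90% probability of detecting a difference between modalities". Neither section mentions an interim look.

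Section 29.2 describes one. Its trigger reads "A futility analysis will be conducted after 50% of the total 18-week RECIST responses (estimated median time to response ~14 weeks", with a gloss that this means N/2 of N. The stopping sentence is: "If at this point the relative risk of no response in the immunotherapy arm over the immunotherapy plus radiation arm is 1.0 or less", then "the study will be stopped for futility". It does not say which response window the comparison uses; the 18-week wording belongs to the trigger.

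On the endpoint, the Protocol Summary says: "The primary endpoint will be BOR (time frame: 96 weeks) rates as evaluated using RECIST version 1.1". Table 18 in section 3.4 reports onset of confirmed nivolumab responses in renal cell carcinoma at a median of 3.0 months, with a range of 1.4 to 13.0 months.

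**The concern.** A futility rule that is obeyed can only remove rejections. Some trials that would have succeeded at 56 per arm are stopped at the halfway look because the combination arm happens to be level or behind. If the stated power is what the final test delivers without a look, the trial as designed must have less.

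Two numbers are then missing for anyone relying on the plan: the power of the design including the rule, and the chance of stopping a combination that truly doubles the response rate. The second matters to the monitoring board, which would be asked to act on the rule.

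**Working it through.** **Inputs.** 56 per arm, 20% against 40%, one-sided level 0.20 (29.0); Fisher's exact test (29.1); halfway look and boundary (29.2). I read N/2 of N as 56 of 112 patients.

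**Step 1: the plan's own figure.** With A and B the final responder counts, A ~ Bin(56, 0.20) and B ~ Bin(56, 0.40), sum the probability of all pairs with one-sided Fisher p ≤ 0.20. Result: **90.2%**. The continuity-corrected two-proportion formula for 90% power also returns exactly 56 per arm. The 90% is thus reproduced with no look, and nothing is set aside for one.

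**Step 2: the boundary.** The ratio is (1 − pA)/(1 − pB) in observed rates, with A immunotherapy alone and B the combination. It is 1.0 or less exactly when the observed rate in A is at least that in B. The trial continues only if the combination is strictly ahead.

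**Step 3: power with the rule, all responses visible.** For nA + nB = 56 patients at the look, sum over interim counts with xB/nB > xA/nA the probability of those counts times the probability that the remaining 56 − nA and 56 − nB patients bring the final Fisher p to 0.20 or below.

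| Look split (A/B) | False stop | Power |
|---|---|---|
| No look | – | 90.2% |
| 28/28 | 6.4% | 87.3% |
| 27/29 | 4.5% | 88.4% |
| 29/27 | 5.0% | 88.2% |
| 25/31 | 4.6% | 88.4% |
| 31/25 | 5.2% | 88.0% |
| Random split of first 56 | 5.2% | 88.0% |

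At 28/28 the loss is 90.2 − 87.3 = 2.9 points. The other 6.4 − 2.9 = 3.5 points of false stops are trials that would have failed at 56 per arm anyway. A simulation of 2,000,000 trials at 28/28 also gives 87.3%.

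**Step 4: the other reading of the trigger.** Expected responses are 56 × 0.20 + 56 × 0.40 = 33.6, and half is 16.8. Triggering the look at 17 responses gives 88.2–88.6% by simulation, depending on how allocation is ordered. The conclusion does not turn on this reading.

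**Step 5: responses that appear after the look.** The endpoint runs to 96 weeks, and 13.0 months is about 13.0 × 52/12 = 56 weeks, so some responses may not yet be visible. The documents do not give the visible share; the following are assumptions, not estimates.

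- Equal share in both arms: 89% visible gives 86–87% power; 80% visible gives 84–86%.
- 100% visible with immunotherapy alone and 90% with the combination: 83.6–85.7% (splits 28/28, 27/29, 29/27).
- The reverse: 88.4–89.1%.

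The 89% case is one illustration of the response-to-date reading: exponential onset with the 14-week median, and accrual of 40 a year ("Forty patients per year will be randomized to the trial over ~ 3 years of accrual"). Patient i of 56 then has 18 + (56 − i) × 52/40 weeks at the look, and the mean of 1 − 2^(−t/14) is 0.886.

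**Step 6: type I error at 20% against 20%, all responses visible.** 14.5% without the look; with it, 12.9% at 28/28 and up to 13.5% at the other listed splits.

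**The case against.** **The power sentences are conditional on 56 per arm.** Read literally, they describe the completed comparison, for which 90% is right. That shows where the figure came from, but it does not rescue it. Section 29.1 presents 90% as the probability of detecting a difference, and the rule can end this trial before 56 per arm is reached.

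**The effect is small.** This stands. No section fixes an exact 28/28 split at the look, and 87.3% is the lowest full-visibility figure found. It also depends on ties: if ties continued, 28/28 would give 89.0%. Most readings lie about 2 points below the fixed-design figure, in a phase II trial run at one-sided 20%.

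**Another test could produce 90% with the rule.** An uncorrected z-test with the stop at 28/28 gives 89.6%. But 29.1 names Fisher's exact test, and 56 is the continuity-corrected fixed-design size.

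**The rule might be meant as non-binding.** Then 90% would stand. The text says the study will be stopped, and nothing else in the document softens it.

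**A reader might go further and infer that true power is near or below 80%.** Under exponential onset from time zero with a 14-week median, 1 − 2^(−18/14) = 59% of responses are visible by 18 weeks, and power is 79–83%. The documents do not support this as an estimate. They give no onset curve, the first scan is at Day 63, and Table 18 has no onset before 1.4 months. Keeping the 14-week median but starting onset at 6.1 weeks (1.4 months) or 9 weeks raises 18-week visibility to 65% or 71%. Nor does 29.2 say that the comparison uses 18-week response.

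**Conclusion.** The point holds and is modest in size. The stated 90% is the fixed-design figure. With the rule as written, a look at 56 of 112 patients and every best overall response visible, overall power is about 87–88% (87.3% at 28/28, 88.0–88.4% at the unequal splits tried, up to about 88.6% if a response count triggers the look). That is a loss of about 1.5–3 points. The chance of wrongly stopping a combination with a true 40% rate is about 4.5–6.4%. These figures assume that the rule is followed, that ties stop and that the true rates are 20% and 40%.

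Three stronger inferences should be resisted. The 87–88% is not an upper bound: unequal visibility favouring the combination gives up to 89.1%. A figure well below it depends on a visible share that the documents do not give. And the shortfall does not show that the trial is too small for its purpose or that its error rate is inflated; type I error falls slightly. Until 29.2 names the response window, the exact power with the rule cannot be computed from the plan.

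**What to change.** - **29.0 and 29.1:** label 90% as fixed-design power. Add that overall power with the 29.2 rule is about 87–88% if all responses are visible at the look, without presenting that as a maximum. Give the chance of wrongly stopping at 20% against 40% (about 4.5–6.4% on the same basis) and the visibility assumption used.
- **29.2:** state whether the stopping comparison uses 18-week response or response to date, and recompute the figures on that window. If the sponsor means the rule to be non-binding, say so; 90% may then stay, with that condition attached.

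The cost is a few sentences and a slightly less favourable stated power. The sample size, final test and boundary stay as they are.
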